Appendix 1.4 Ethical Considerations

Informed Consent

It is the responsibility of the investigator to obtain written informed consent from all study subjects prior to any study-related procedures including screening assessments. All consent documentation must be in accordance with applicable regulations and GCP. Each subject or the subject's legally-authorized representative, as applicable, is requested to sign and date the subject informed consent form or a certified translation if applicable, after the subject has received and read (or been read) the written subject information and received an explanation of what the study involves, including but not limited to: the objectives, potential benefits and risk, inconveniences, and the subject's rights and responsibilities. A copy of the informed consent documentation (ie, a complete set of subject information sheets and fully executed signature pages) must be given to the subject or the subject's legally authorized representative, as applicable. This document may require translation into the local language. Signed consent forms must remain in each subject's study file and must be available for verification at any time.

The principal investigator provides the sponsor with a copy of the consent form which was reviewed by the IRB/EC and which received their favorable opinion/approval. A copy of the IRB/EC's written favorable opinion/approval of these documents must be provided to the sponsor, prior to the start of the study unless it is agreed to and documented (abiding by regulatory guidelines and national provisions) prior to study start that another party (ie, sponsor or coordinating principal investigator) is responsible for this action. Additionally, if the IRB/EC requires modification of the sample subject information and consent document provided by the sponsor, the documentation supporting this requirement must be provided to the sponsor.

Institutional Review Board or Ethics Committee

For sites outside the EU, it is the responsibility of the investigator to submit this protocol, the informed consent document (approved by the sponsor or their designee), relevant supporting information and all types of subject recruitment information to the IRB/EC for review, and all must be approved prior to site initiation.

The applicant for an EC opinion can be the sponsor or the investigator for sites within the EU; for multicenter studies the applicant can be the coordinating principal investigator or sponsor, according to national provisions.

Responsibility for coordinating with IRBs/ECs is defined in the clinical trial agreement.

Investigational product supplied will not be released until the sponsor has received written IRB/EC approval.

Prior to implementing changes in the study, the sponsor and the IRB/EC must approve any revisions of all informed consent documents and amendments to the protocol unless there is a subject safety issue. If required by local law, substantial amendments to the protocol must also be approved by the appropriate regulatory agency prior to implementation.

For sites outside the EU, the investigator is responsible for keeping the IRB/EC apprised of the progress of the study and of any changes made to the protocol, at least annually or more frequently in accordance with the requirements, policies, and procedures established by the IRB/EC. This can be the responsibility of the sponsor or investigator for sites within the EU; or for multicenter studies, the coordinating principal investigator, according to national provisions. The investigator must also keep the local IRB/EC informed of any serious and significant AEs as required by IRB/EC procedures.

Privacy and Confidentiality

All US-based sites and laboratories or entities providing support for this study, must, where applicable, comply with the Health Insurance Portability and Accountability Act (HIPAA) of 1996. A site that is not a covered entity as defined by HIPAA must provide documentation of this fact to the sponsor.

The confidentiality of records that may be able to identify subjects will be protected in accordance with applicable laws, regulations, and guidelines.

After subjects have consented to take part in the study, the sponsor and/or its representatives' reviews their medical records and data collected during the study. These records and data may, in addition, be reviewed by others including the following: independent auditors who validate the data on behalf of the sponsor; third parties with whom the sponsor may develop, register, or market maribavir; national or local regulatory authorities; and the IRB/EC which gave approval for the study to proceed. The sponsor and/or its representatives accessing the records and data will take all reasonable precautions in accordance with applicable laws, regulations, and guidelines to maintain the confidentiality of subjects' identities.

Subjects are assigned a unique identifying number.

The results of studies containing subjects' unique identifying number, relevant medical records, and possibly initials and dates of birth, where allowed per local law, may be transferred to, and used in, other countries which may not afford the same level of protection that applies within the countries where this study is conducted. The purpose of any such transfer would include: to support regulatory submissions, to conduct new data analyses to publish or present the study results, or to answer questions asked by regulatory or health authorities.

Study Results / Publication Policy

The term “Publication” shall mean any paper, article, manuscript, report, poster, internet posting, presentation slides, abstract, outline, video, instructional material, presentation (in the form of a written summary), or other public disclosure of the study results, in printed, electronic, oral, or other form. The parties understand and agree that participation in the study may involve a commitment to publish the data from all sites participating in the study in a cooperative publication with other investigators prior to publication or oral presentations of the study results on an individual basis. The site agrees not to publish or present the site’s study results until such time as either the aggregate multi-site study results are published in a cooperative publication or for a period of one (1) year after termination or completion of the study at all participating sites, whichever shall first occur. After that time, the site may publish the site’s study results in scientific journals or present the study results at symposia or other professional meetings in accordance with the following provisions:

If the study is part of a multicenter study, the first publication of the study results shall be made by the sponsor in conjunction with the sponsor’s presentation of a joint, multicenter publication of the compiled and analyzed study results. If such a multicenter publication is not submitted to a journal for publication by the sponsor within an 18-month period after conclusion, abandonment, or termination of the study at all sites, or after the sponsor confirms there shall be no multicenter study publication of the study results, an investigator may individually publish the study results from the specific site in accordance with this section. The investigator must, however, acknowledge in the publication the limitations of the single site data being presented.

At least sixty (60) days prior to submitting an abstract, manuscript, or other document for publication, a copy of the proposed publication will be provided to the sponsor by the site for review. Upon the sponsor’s request, the site agrees to remove any and all confidential information (expressly excluding study results) identified in the publication and to delay such submission or presentation for an additional sixty (60) day period in order to allow the sponsor time to file any patent application(s). All publications of the study results shall appropriately reference the multi-site study publication, if any, or the fact that the study results are a subset of data resulting from a larger multi-site study.

Shire is committed to transparent dissemination of all scientific, technical and medical manuscripts generated from Shire-supported research. Therefore, after January 1, 2018, Shire will require the submission of all Shire-supported research manuscripts to journals that offer public availability via Open Access (including publisher platforms/repositories and self-archiving). Open Access refers to the free at point of entry, online availability of published research output with, where available, rights of re-use according to an End User License.

Unless otherwise required by the journal in which the publication appears, or the forum in which it is made, authorship will comply with the International Committee of Medical Journal Editors (ICMJE) Recommendation for the Conduct, Reporting, Editing and Publication of Scholarly Work in Medical journals. Participation as an investigator does not confer any rights to authorship of publications.

Appendix 2 Adverse Events: Definitions and Procedures for Recording, Evaluating, Follow-Up, and Reporting

Appendix 2.1 Adverse Event Definitions

An AE is any untoward medical occurrence in a clinical investigation subject administered a pharmaceutical product and that does not necessarily have a causal relationship with this IP or medicinal product. An AE can therefore be any unfavorable and unintended sign (including an abnormal laboratory finding), symptom, or disease temporally associated with the use of a medicinal (investigational) product, whether or not related to the medicinal (investigational) product (ICH Guidance E2A 1995).

Treatment-emergent Adverse Event

A TEAE is defined as any event emerging or manifesting at or after the initiation of treatment with an IP or medicinal product or any existing event that worsens in either intensity or frequency following exposure to the IP or medicinal product.

Serious Adverse Event

An SAE is any untoward medical occurrence (whether considered to be related to IP or not) that at any dose:

- Results in death
- Is life-threatening. Note: The term ‘life-threatening’ in the definition of “serious” refers to an event in which the subject was at risk of death at the time of the event; it does not refer to an event which hypothetically might have caused death if it was more severe.
- Requires inpatient hospitalization or prolongation of existing hospitalization. Note: Hospitalizations, that are the result of elective or previously scheduled investigations procedures or surgery for pre-existing conditions and have not worsened after initiation of treatment, should not be classified as SAEs. For example, an admission for a previously scheduled ventral hernia repair would not be classified as an SAE; however, complication(s) resulting from a hospitalization for an elective or previously scheduled surgery that meet(s) serious criteria must be reported as SAE(s).
- Results in persistent or significant disability/incapacity
- Results in a congenital abnormality/birth defect
- Is an important medical event. Note: Important medical events that may not result in death, be life-threatening, or require hospitalization may be considered an SAE when, based upon appropriate medical judgment, they may jeopardize the subject and may require medical or surgical intervention to prevent 1 of the outcomes listed in this definition. Examples of such medical events include bronchospasm associated with anaphylaxis requiring intensive treatment in an emergency room or at home; blood dyscrasias or convulsions that do not result in inpatient hospitalization; or the development of drug dependency or drug abuse.

Unexpected Adverse Event

An unexpected adverse event is an AE whose nature, severity, specificity, or outcome is not consistent with the term, representation, or description used in the IB. “Unexpected” also refers to the AEs that are mentioned in the maribavir IB and/or prescribing information as occurring with a class of drugs or as anticipated from the pharmacological properties of the product, but are not specifically mentioned as occurring with the particular product under investigation.

The expectedness of AEs will be determined by the sponsor using the IB and/or prescribing information as the Reference Safety Information. This determination will include considerations such as the number of AEs previously observed, but not on the basis of what might be anticipated from the pharmacological properties of a product.

Suspected Unexpected Serious Adverse Reaction

A Suspected Unexpected Serious Adverse Reaction (SUSAR) is defined as any suspected adverse reaction to study treatment (ie, including active comparators) that is both serious and unexpected.

The event(s) must meet all of the following:

- Suspected adverse reaction
- Serious
- Unexpected
- Assessed as related to study treatment

Unanticipated Adverse Device Effect

An unanticipated adverse device effect is any serious adverse effect on health or safety or any life-threatening problem or death caused by, or associated with, a device, if that effect, problem, or death was not previously identified in nature, severity, or degree of incidence in the study protocol or product labeling; or any other unanticipated serious problem associated with a device that relates to the rights, safety, or welfare of subjects.

Clinical Laboratory and Other Safety Assessment

A change in the value of a clinical laboratory parameter, vital sign measure, or ECG assessment can represent an AE if the change is clinically relevant or if, during administration of IP, a shift of a parameter is observed from a value in the normative range to a value that is outside the normal range and considered clinically significant, or a further waning of an already clinically significant value. When evaluating such changes, the extent of deviation from the reference range, the duration until return to the reference range, either while continuing administration or after the end of administration with the IP, and the range of variation of the respective parameter within its reference range, should also be considered.

If, at the end of the treatment phase, there are abnormal clinical laboratory (such as hematology panel or clinical chemistry panel), vital sign, or ECG values which were not present at the pretreatment evaluation observed closest to the start of study treatment, further investigations should be performed until the values return to within the reference range or until a plausible explanation (eg, concomitant disease or expected disease evolution) is found for the abnormal values.

The investigator should assess, based on the above criteria and the clinical condition of the subject, whether a change in a clinical laboratory value, vital sign, or ECG parameter is clinically significant and represents an AE.

Appendix 2.2 Collection of Adverse Events

All AEs/SAEs are collected from the time the informed consent is signed until the defined follow-up period stated in Section 7.1.4. This includes events occurring during the screening phase of the study, regardless of whether or not IP is administered.

All AEs/SAEs must be followed to closure (the subject's health has returned to his/her baseline status or all variables have returned to baseline), regardless of whether the subject is still participating in the study. Closure indicates that an outcome is reached, stabilization achieved (the investigator does not expect any further improvement or worsening of the event), or the event is otherwise explained.

Appendix 2.3 Assessment of Adverse Events

Severity Categorization

The severity of AEs must be recorded during the course of the event including the start and stop dates for each change in severity. An event that changes in severity is captured as a new event. Worsening medical conditions, signs or symptoms present prior to initiation of IP, must be recorded as new AEs.

For example, if a subject reports mild intermittent dyspepsia prior to initiation of dosing with the IP, and the dyspepsia becomes severe and more frequent after first dose of a new AE of severe dyspepsia (with the appropriate date of onset) should be documented in the source.

The medical assessment of severity is determined by using the following definitions:

- Mild:** A type of AE that is usually transient and may require only minimal treatment or therapeutic intervention. The event does not generally interfere with usual activities of daily living.
- Moderate:** A type of AE that is usually alleviated with specific therapeutic intervention. The event interferes with usual activities of daily living, causing discomfort but poses no significant or permanent risk of harm to the research subject.
- Severe:** A type of AE that interrupts usual activities of daily living, or significantly affects clinical status, or may require intensive therapeutic intervention.

Relationship Categorization

A physician/investigator must make the assessment of relationship to IP for each AE. The investigator should decide whether, in his or her medical judgment, there is a reasonable possibility that the event may have been caused by the IP. If there is no valid reason for suggesting a relationship, then the AE should be classified as “not related”. Otherwise, if there is any valid reason, even if undetermined or untested, for suspecting a possible cause-and-effect relationship between the IP and the occurrence of the AE, then the AE should be considered “related”. The causality assessment must be documented in the source.

The following additional guidance may be helpful:

Term	Relationship Definition
Related	The temporal relationship between the event and the administration of the IP is compelling and/or follows a known or suspected response pattern to that product, and the event cannot be explained by the subject’s medical condition, other therapies, or accident.
Not Related	The event can be readily explained by other factors such as the subject’s underlying medical condition, concomitant therapy, or accident and no plausible temporal or biologic relationship exists between the IP and the event.

Outcome Categorization

The outcome of AEs must be recorded in the source during the course of the study. Outcomes are as follows:

- Fatal
- Not Recovered/Not Resolved
- Recovered/Resolved
- Recovered/Resolved With Sequelae
- Recovering/Resolving
- Unknown.

If applicable, action taken (ie, dose increased, dose not changed, dose reduced, drug interrupted, drug withdrawn, not applicable, or unknown) will also be recorded on the AE CRF.

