### 2.2.2 Exploratory Pharmacokinetic Endpoints

### 2.2.3 Safety Endpoints

The safety analysis will be performed using the Safety Analysis Set. Safety endpoints include AEs, vital signs, ECG variables, and clinical laboratory variables. The following safety evaluations will be performed:

- Number, severity, seriousness, and causality of treatment-emergent adverse events (TEAEs).
- Changes in vital signs, ECGs, and clinical laboratory results (hematology, chemistry, and urinalysis) from baseline to post-baseline time points.

For each safety variable, the last value collected before the first dose of investigational product in that period will be used as baseline for all analyses of that safety variable in that period.

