### 7.1 Adverse Events

Adverse events will be coded using MedDRA Version 23.0 or newer.

An AE (classified by preferred term) that occurs during the study will be considered a TEAE if it has a start date on or after the first dose of investigational product or if it has a start date before the date of the first dose of investigational product, but increases in severity on or after the date of the first dose of investigational product. If more than 1 AE with the same preferred term is reported before the date of the first dose of investigational product, then the AE with the greatest severity will be used as the benchmark for comparison to the AEs occurring during the study under the preferred term. Adverse events during the study will be assigned to the treatment(s) a subject has taken at the onset of the event. An AE with start date and time during the wash-out period or the 7 days follow-up period after last single dose of IP will be assigned to the prior treatment subject received. An AE that occurs more than 7 days after the date of the last dose of investigational product will not be counted as a TEAE.

An overall summary of the number of subjects with TEAEs as well as the number of events will be presented, including the number and percentage of subjects with any TEAEs, serious TEAEs, TEAEs related to investigational product and TEAEs leading to discontinuation of investigational product.

The number and percentage of subjects reporting TEAEs, as well as the number of events, in each cohort, each treatment group, and overall will be tabulated by system organ class (SOC) and preferred term (PT); by SOC, preferred term (PT), and maximum severity. TEAEs considered related to investigational product will also be summarized by SOC and preferred term. If more than 1 AE occurs with the same preferred term for the same subject, then the subject will be counted only once for that preferred term using the most severe and most related occurrence for the summarization by severity and by relationship to investigational product. Presentation by SOC and PT will present SOC sorted alphabetically and PT within SOC by descending incidence.

TEAEs and related TEAEs will be summarized by preferred term by descending frequency. Serious TEAEs, TEAEs leading to discontinuation of investigational product and serious TEAEs leading to death, will be summarized by SOC, preferred term, cohort, and treatment group.

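### Each change in AE severity becomes a separately dated event with no rule linking records of one episode, so TEAE event counts are inflated and an AE that only eases after a Period 2 or 3 dose is charged to that dose

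*Protocol*

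**What the plan says.** **Capture.** Protocol Appendix 2.3 asks for severity to be recorded throughout an event, "including the start and stop dates for each change in severity", and adds: "An event that changes in severity is captured as a new event". The rule is not limited to worsening. The following sentence deals separately with worsening of conditions present before dosing.

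**TEAE status.** Under SAP 7.1 an AE "will be considered a TEAE if it has a start date on or after the first dose of investigational product". An AE that began earlier also qualifies if it "but increases in severity on or after the date of the first dose of investigational product". Where more than one AE of a preferred term was reported before the first dose, "then the AE with the greatest severity will be used as the benchmark for comparison to the AEs occurring during the study". The window closes 7 days after the last dose. Protocol Appendix 2.1 counts a pre-existing event only when it worsens: "any existing event that worsens in either intensity or frequency following exposure".

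**Dose assignment.** SAP 7.1: "Adverse events during the study will be assigned to the treatment(s) a subject has taken at the onset of the event".

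**Counting.** The number of TEAEs is a listed safety endpoint (SAP 2.2.3). SAP 7.1 and Protocol 8.8 report event numbers alongside subject numbers. SAP 7.1 counts a subject once per preferred term, at the worst severity and closest relationship. Neither SAP 7.1 nor the data-handling conventions in SAP 12 say how to treat several records of one continuous episode.

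**The concern.** The capture rule and the analysis rule each make sense alone but do not fit together. Capture splits an episode into severity segments, each with its own start date. The analysis treats each start date as an onset.

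Two consequences follow. First, the tabulated number of events partly reflects how often severity was re-graded. Second, in the Japanese cohort a segment that begins after the Period 2 or 3 dose only because the AE became milder has its onset under that dose. It then appears in the 200 or 800 mg column as if it had emerged there. Those columns describe tolerability across doses in a study meant to inform dose selection for Japanese patients.

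There is also a gap for AEs already present before the first dose. The start-date limb points one way. The benchmark sentence and Appendix 2.1 point the other.

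**Working it through.** The plan gives no figure that depends on this point, so there is none to reproduce. The check applies the written rules to constructed cases and then shows a range for the event count.

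**Inputs from the documents.**
- 12 subjects per cohort (SAP 3.4).
- 72 to 73 hours between doses in Japanese subjects (Protocol Table 1).
- Dysgeusia in up to 80% of subjects in single-dose studies, resolving in about 8 hours, range 0.5 to 25 (Protocol 1.2.5).

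**Step 1: four AE courses.** Each is one preferred term in one subject, with doses at 0 and 72 hours. The benchmark column assumes that a single pre-dose AE serves as its own benchmark, although the SAP sentence is worded for more than one. The last column applies the rules under the fix.

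| Course | TEAE records by start date | With pre-first-dose benchmark | With the fix |
|---|---|---|---|
| A. Mild at 0.5 h, moderate at 2 h, mild at 5 h | 3 | 3 | 1 |
| B. Moderate before first dose, mild at 3 h | 1 | 0 | 0 |
| C. Moderate at 60 h, mild at 80 h | 2: one under 400 mg, one under the Period 2 dose | 2 | 1, under 400 mg |
| D. Mild before first dose, severe at 2 h, mild at 6 h | 2 | 1 | 1 |

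In A the subject is counted once under 400 mg either way, so only the event count changes. In C the subject enters the incidence of both doses. The benchmark does not help there, because it refers only to the time before the first dose of the study.

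**Step 2: size of the event-count inflation.** Let q be the share of episodes that change severity and m the number of extra records per such episode. Both are assumptions. The inflation factor is 1 + q × m. Expected dysgeusia episodes per dose at the 80% upper figure are 0.80 × 12 = 9.6.

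| q | m | Factor | Events |
|---|---|---|---|
| 10% | 1 | 1.10 | 10.6 |
| 25% | 1 | 1.25 | 12.0 |
| 50% | 2 | 2.00 | 19.2 |
| 100% | 2 | 3.00 | 28.8 |

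Expected subjects with dysgeusia stay at 9.6 in every row.

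**Step 3: size of a cross-dose assignment.** One extra subject in a 12-subject column is 1/12 = 8.3 percentage points. The AE must still be present at least 72 hours after the previous dose. The longest dysgeusia duration quoted is 25 hours, so this concerns longer-lasting AEs. The documents give no frequency for them.

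**The case against.** The strongest reply is that the main safety outputs are protected. Subject incidence within a dose is not inflated, because of the once-per-preferred-term rule. Safety is descriptive, and no test or decision rule uses event counts. The same capture rule applies to both cohorts, so at 400 mg it distorts the comparison of event counts only if severity changes at different rates in the two cohorts. This stands, and it limits the importance of the point.

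A reader might infer that any AE already present before the first dose that then eases becomes a TEAE. The documents do not settle this. Under Appendix 2.3 a single record never changes severity, so the SAP's severity-increase limb and its benchmark make sense only at preferred-term level. At that level moderate-to-mild is not emergent, and Appendix 2.1 agrees. This is a conflict to reconcile, not an established error.

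A reader might also infer that wrong dose assignment affects the direct comparison of the cohorts. It does not: Caucasian subjects receive one dose, and 400 mg is always Period 1 in Japanese subjects, so no earlier AE can carry over into either 400 mg column.

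Finally, linking conventions may exist in the separate table specifications or the CRF Completion Guidelines, which were not available here. That lowers confidence that no rule exists anywhere. It does not remove the need for one in the SAP, where the TEAE and counting rules are set.

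**Conclusion.** The point holds for two mechanisms. Event counts are inflated whenever an episode changes severity after dosing within the TEAE window. In Japanese subjects, an AE that only eases after the Period 2 or 3 dose is assigned to that dose, and nothing in SAP 7.1 prevents it.

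The inflation factor of 1.1 to 3.0 is illustrative. A doubling of counts should not be read as expected: it requires half of all episodes to rise and fall in severity, and scheduled AE queries on the detailed schedules are few (predose, at dosing, 3 and 24 hours), so many short changes would depend on spontaneous reports. The 8.3-point figure is per affected subject and assumes all 12 are dosed in that period.

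The PK analyses are unaffected. The change should be made before database lock, because it concerns a named endpoint and the dose columns, but its weight is moderate.

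**What to change.** Keep the capture rule and show every record in the listings. Add to SAP 7.1:

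- **(a) Linking.** Records of the same subject and preferred term, where one stops as the next starts, form a chain. A chain is one event, at its maximum severity.
- **(b) Emergence.** A severity-change record is treatment-emergent for a dose only if its severity exceeds that present just before that dose. The benchmark is reset before each period's dose. State that this governs over the start-date limb for AEs present before the first dose, which reconciles it with Appendix 2.1.
- **(c) Assignment.** A chain belongs to the dose at its first onset, and also to a later dose if it worsens after that dose. The overall column counts it once, with a footnote that the dose columns may not sum to the total.

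Start and stop dates and severity are already collected, so a derivation in the analysis dataset is enough; a linking field on the AE CRF is optional. The cost is a few SAP sentences, a little more programming, and event counts that differ from the raw number of records.
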